One approach that holds considerable promise is the use of a relatively new class of drugs used to treat type 2 diabetes mellitus (T2DM), specifically sodium–glucose co-transporter 2 (SGLT-2) inhibitors (gliflozin class). A major driver for the use of these drugs in the setting of HF is the EMPA-REG OUTCOME trial. This was the first large randomized clinical trial that showed empagliflozin (EMPA), a specific SGLT-2 inhibitor, was not only effective in reducing MACE but that the outcome was driven primarily by a reduction in cardiovascular deaths and hospitalization for heart failure.(2)

Myocardial metabolic remodeling is integral to HF development, with a shift from free fatty acids (FFA) utilization (which produce many ATP (adenosine triphosphate) molecules but also requires many oxygen molecules) in healthy myocardium toward glucose consumption (which produce less ATP but is more oxygen-efficient in failing hearts. Although past research focused exclusively on FFA and glucose, the heart possesses metabolic flexibility and is an omnivore capable of oxidizing other substrates such as ketone bodies (KB), lactate, and branched-chain amino acid (BCAA). Importantly, KB are the most energetically efficient fuel because they produce many ATP molecules while showing the lowest oxygen requirements. Of note, empagliflozin-induced glycosuria reduces both plasma glucose and insulin levels and increases both lipolysis and plasma glucagon concentration (thus resembling fasting state), which causes ketogenesis and hyperketonemia. (3)

Accurate measurements of left ventricular volumes and function are important in the management of patients with various cardiac abnormalities. M mode and cross-sectional echocardiography are the most commonly used methods to measure left ventricular volumes and function.(4)

Recently, improvements in 2D echocardiographic image resolution have enabled detection of tissue pixels and tracking of these acoustic markers from frame to frame. The tissue velocity is estimated from the local frame-to-frame displacement; the automatic evaluation of the velocity at a point is determined by comparison of the displacement of the image data around that point in two consecutive frames. These methods have been used, in several different formulations, in many research fields and fall in the category known as Optical Flow commonly referred as Speckle Tracking in ultrasound imaging. (5)

Speckle tracking echocardiography has shown to be accurate in detecting subclinical myocardial dysfunction when most of the conventional echocardiograph parameters were normal or reported inconsistent results.(6)

2. AIM/ OBJECTIVES

The study aims to compare the doses of 10 versus 25 milligrams of Empagliflozin among diabetic patients with Anterior STEMI with reduced LVEF who underwent PPCI regarding MACE and LV remodeling for 6 months duration.

3. Methodology:

- **Type of Study:** a prospective clinical trial.
- **Study Setting:** Patients presenting to Ain shams university hospitals
- **Study Population:** anterior STEMI patients
- **Study Period:** 6 months
- **Sample Size:** Patients diagnosed with anterior STEMI in the ER fulfilling the inclusion criteria. (200 patients) divided into two groups the first will receive 10 mg of Empagliflozin and the other will receive 25 mg.
- **Ethical considerations:**
The clinical research study will be conducted in accordance with the current policies, requirements, and regulations of Ain Shams University. Information will be recorded in an appropriate manner to ensure that potential subjects or their authorized representatives are fully aware of the nature and objectives of the clinical study, and the potential risks and benefits of participating in the study. Written informed consent will be obtained from each patient or their authorized representative, prior to any study procedures being carried out.
- **Inclusion Criteria:**

- 1- Diabetic patients with anterior STEMI with reduced LVEF who underwent PPCI with successful revascularization and resulting into TIMI III flow and who are receiving SGLTi for the first time.

Exclusion Criteria:

- 1- patients who did not undergo primary PCI, those treated medically or had thrombolysis
- 2- Non diabetic patient.
- 3- Diabetic patient already on SGLTi
- 4- STEMIs other than anterior.
- 5- NSTEMI patients.
- 6- Patients having valvular heart diseases.
- 7- Patients having renal impairment.
- 8- Patients with LV myopathies of non-ischemic origin.

4. Study Tools:

A- history taking: including

- a- personal history" name, age, marital status and special habits of medical importance e.g smoking and alcohol consumption "
- b- past history with special comment on diabetes and other comorbidities e.g hypertension, CKD and dyslipidemia

- c- History of present illness with special comment on pain to door interval.
- d- Positive family history.
- e- Drug history: and to make sure whether patients are receiving SGLTi or not.

B- Examination:

- 1- General examination: including vital signs and complexion.
- 2- Local examination including heart and chest auscultation.

C- ECG: all patients will have 12 lead surface ECG at start of the study and during follow up.

D- Echocardiographic Assessment:

1- Standard transthoracic 2D echocardiographic examination:

Standard 2D echocardiography will be performed using GE vivid E70 echocardiography machine; the whole study will be ECG gated in supine or left lateral position. Standard images will be obtained in the parasternal (long- and short-axis views) and apical (2, 3, 4, and 5-chamber images) views. Standard 2D and color Doppler data, triggered to the QRS complex, will be saved in cine-loop format.

M-mode, 2D, TDI as well as pulsed and continuous Doppler flow across the different heart valves in all the standard views will be done according to the recommendations of the American Society of Echocardiography (7).

Heart failure with reduced ejection fraction (HFrEF) was defined as EF less than 40% , Also referred to as systolic HF. Randomized controlled trials have mainly enrolled patients with HFrEF, and it is only in these patients that efficacious therapies have been demonstrated to date.(8)

The definition of left ventricular remodeling using cardiac magnetic resonance following ST-elevation myocardial infarction is highly variable, among studies including highly selected patients. The most frequent left ventricular remodeling criterion were a 20% increase in end-diastolic volumes or a 15% increase in end-systolic volumes.(9)

A composite cut-off value of a 12% to 15% increase in end-systolic volume and a 12% to 20% increase in end-diastolic volume using a follow-up cardiac magnetic resonance imaging 1 to 3 months after myocardial infarction might be proposed as a consensual cut-off for defining adverse left ventricular remodeling.(9)

The following measurements will be focused on and recorded:

1- Assessment of LV systolic function :

By applying M-Mode modality to LV in parasternal long axis view, we will measure LV end-diastolic diameter (EDD), LV end-systolic diameter (ESD), IVS and PWT in both systole and diastole LVEF and FS. Also estimation of EF by Simpson biplane method and 2D will be done.

2- LA dimension measurement:

Left Atrial dimensions and aorta: The anteroposterior diameter of the left atrium will be measured in the parasternal long-axis view using M mode perpendicular to the aortic root long axis at the level of the aortic sinuses by using the leading-edge to leading-edge convention.

3- Wall motion abnormalities:

Using 2D echocardiography in apical and para- sternal windows to assess RSWMA.

4- Assessment of LV diastolic function:

Pulsed-wave (PW) Doppler will be applied in the apical 4-chamber view to obtain mitral inflow velocities and assess LV filling. The following measurements of mitral inflow will be recorded: the peak early filling (E-wave) and late diastolic filling (A-wave) velocities, the E/A ratio.

Tissue Doppler imaging (TDI): in apical 4- chamber view, TDI will be applied in the pulse-Doppler mode to allow for a spectral display and recording of mitral annulus velocities at the lateral mitral annulus, medial mitral annulus, and the mean value will be recorded. The measurements obtained are Systolic velocity of the mitral annulus (S), early diastolic annular velocity (E'), and late diastolic annular velocity (A'). The average of 3 readings of lateral E' will be recorded. E/E' ratio (mitral peak early filling velocity/peak mitral lateral annular velocity in early diastole) will be automatically calculated.

5- Assessment of RV systolic function:

The TAPSE method is a relatively simple technique used to assess RV longitudinal performance. To perform this measurement, an M-mode cursor will be aligned through the lateral tricuspid annulus in the apical four-chamber view and measurement of the amount of longitudinal motion of the annular plane in systole. TAPSE < 17 mm suggests RV dysfunction.

Also, TDI will be applied in the pulse-Doppler mode to allow for a spectral display and recording of tricuspid annulus velocities at the lateral tricuspid annulus in apical 4 chamber view to assess S of RV with value less than 9.5 suggestive of RV dysfunction.

E- Speckle tracking echocardiography of the left ventricle:

speckle tracking could be used as a predictor for LV remodeling post myocardial infarction with best cut-off value was >12.5 (Sensitivity 87%, Specificity 85%).(10)

Loops of multiple ECG- gated entire cardiac cycles of the LV from apical 4, 3 and 2 chamber, parasternal long and short axis views will be obtained. The recorded data will be stored and later analyzed with the offline-workstation software EchoPAC Dimension [12.0, General Electrics (GE) Medical Systems GmbH, Germany].

In the end-systolic frame, the endocardial border is traced beginning at one end of the mitral annulus and ending at the other end in each of the apical views.

The software then generates a region-of-interest (ROI) to include the entire myocardial thickness. The width of the ROI can be manually adjusted as required. Care should be taken to avoid including bright, echogenic pericardium in the ROI.

The software then divides the LV myocardium into six segments and generates segmental and global longitudinal strain. As the myocardium usually shortens in the longitudinal direction during systole, the longitudinal strain is displayed below the baseline.

From these curves, peak systolic longitudinal strain is recorded for each of the myocardial segments. The strain values for all the segments are recorded and averaged to obtain the global longitudinal strain (GLS). A topographic representation of the regional and global longitudinal strain of all 17 analyzed segments (Bull's eye configuration) is then automatically generated.

F- 2D Speckle Tracking Echocardiography of the left Atrial Phasic functions (apical four chamber view and apical two chamber view) Parameters:

- Left Atrial Strain during Reservoir phase (LASr): Reflects the left atrium's ability to store blood during ventricular systole.
- Left Atrial Strain during Conduit phase (LAScd): Assesses the passive filling of the left ventricle during early diastole.
- Left Atrial Strain during Contraction phase (LASct): Evaluates the active contraction of the left atrium during late diastole.
- Left atrial maximum volume (LAVmax): It is measured just before the mitral valve opens, at the end of left ventricular systole.

G- Major adverse cardiac events (MACE): composite point of death, repeated hospitalization, re-infarction and new onset heart failure will be observed for six months post catheterization and initiation of SGLTi.

H- Follow up: patients will be followed up for 6 months regarding symptoms and MACE. All echocardiographic study parameters will be repeated at the end of the study period.

5-Statistical Analysis:

All data will be statistically analyzed to compare results in different time (day one then 6 months later)

6. References:

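### No primary outcome: the aim joins MACE and LV remodeling unranked, remodeling has no adopted definition, and no between-dose test is named, so the deciding measure can be chosen after the results are seen

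*Protocol*

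**What the plan says.** Section 2 (Aim/Objectives) sets a dose comparison "regarding MACE and LV remodeling for 6 months duration". The two outcomes are joined by a conjunction, and nothing in the protocol text available calls any outcome primary or secondary.

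The sample size item in section 3 gives "200 patients) divided into two groups the first will receive 10 mg of Empagliflozin and the other will receive 25 mg". It ties that number to no outcome, effect size, power or significance level.

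Section 4, part D, reports remodeling cut-offs from a review of cardiac magnetic resonance studies, as ranges of increase in end-systolic and end-diastolic volume. It does not adopt one for this trial, which measures by echocardiography. Parts D to F then list many parameters, starting with "LV end-diastolic diameter (EDD), LV end-systolic diameter (ESD), IVS and PWT in both systole and diastole LVEF and FS" and continuing through "Also estimation of EF by Simpson biplane method and 2D will be done" to wall motion, mitral inflow, annular velocities, RV function, LV strain and left atrial strain and volume. Part H adds: "All echocardiographic study parameters will be repeated at the end of the study period".

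Section 5 is a single sentence: "All data will be statistically analyzed to compare results in different time (day one then 6 months later").

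**The concern.** The trial exists to say whether one dose does better than the other. To answer that, the protocol must fix which measure decides, at what time, and by what contrast between the groups. This one fixes none of the three. MACE and remodeling may disagree, and no rule then says which prevails. Remodeling, lacking a definition, can be any of several diameters, volumes, ejection fractions or strain values.

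Two things are at stake. A chance difference on one of several candidate measures could be presented as the trial's answer. MACE could also be promoted to the deciding outcome afterwards, although 200 patients on two active doses give little power for it.

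**Working it through.** **The plan's own figure.** The only design figure is 200 patients. It cannot be reproduced, because no effect size, standard deviation, event rate, significance level or power is given.

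**Assumptions (not in the protocol).** Two-sided 5% per test, no multiplicity adjustment, 100 patients per group, identical doses for the error-rate calculation, and a common correlation r between test statistics.

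**Counting the measures (section 4, parts D to G).**

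- M-mode LV: EDD, ESD, IVS and PWT each in systole and diastole, LVEF, FS = 8
- Simpson EF = 1; LA diameter = 1; wall motion = 1
- E, A, E/A = 3; annular S, E', A' = 3; E/E' = 1
- TAPSE and RV S = 2; GLS = 1
- LASr, LAScd, LASct, LAVmax = 4
- MACE composite = 1

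The total is 26. Counting either the aorta or a separate 2D EF gives 27; counting both gives 28. Segmental strains are left out, and each annular velocity is counted once.

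**The narrower family that the aim names.** MACE (1), the LV measures (8 M-mode + Simpson EF + wall motion + GLS = 11), and change in end-diastolic and end-systolic volume (2, the quantities used in the cited cut-offs): 1 + 11 + 2 = 14.

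**Chance of at least one false dose difference among k tests.**

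Independent tests: 1 − 0.95^k.

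- k = 2: 1 − 0.9025 = 9.75%
- k = 14: 1 − 0.4877 = 51.2%
- k = 27: 1 − 0.2503 = 75.0%

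Equally correlated normal test statistics: 1 − E[{Φ((1.96 − √r·X)/√(1−r)) − Φ((−1.96 − √r·X)/√(1−r))}^k], with X standard normal, integrated numerically.

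| k | r = 0 | r = 0.3 | r = 0.5 | r = 0.7 |
|---|---|---|---|---|
| 2 | 9.8% | 9.5% | 9.1% | 8.3% |
| 14 | 51% | 44% | 35% | 25% |
| 27 | 75% | 63% | 48% | 33% |

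One named primary outcome tested once would hold this at 5%.

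**What 200 patients can show on MACE.** The protocol gives no event rate, so 20% is an assumption. For 20% versus 15%, the mean is 0.175 and the two-proportion formula with pooled variance under the null gives

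Φ[(0.05·√100 − 1.96·√(2·0.175·0.825)) / √(0.20·0.80 + 0.15·0.85)] = Φ[(0.500 − 1.053)/0.536] = Φ(−1.03) ≈ 15%.

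By the same formula, 80% power needs 20% versus 6.6%, or 30% versus 13.7% if the rate is higher. Power is 51% for 20% versus 10% and 72% for 30% versus 15%.

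**What 200 patients can show on one continuous measure.** The detectable difference at 80% power is (1.96 + 0.842)·√(2/100) = 0.40 SD if all 200 have a 6-month value. With 90 per group it is 2.802·√(2/90) = 0.42 SD.

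**The case against.** A reader might infer that section 5 orders a dose comparison on every listed measure. It does not. The sentence goes on to name a comparison of day one with 6 months, and it states no dose contrast, significance level or p-value. Repeated dose testing is a risk that the text leaves open, not something it prescribes.

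A reader might also infer that any of about 27 measures can carry the dose claim. The aim limits the claim to MACE and LV remodeling, so RV and left atrial measures do not plainly qualify. The family of about 14 is the fairer one, and even that includes two volumes absent from the list of recordings. The 27-measure figures are an outer case.

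Nor do the documents show that a false positive is likely. Several measures are functions of others: FS of EDD and ESD, E/A of E and A, and more than one estimate of the same EF. Independence is therefore the least realistic case. At correlation 0.5 the chance is below one half even for 27 tests. The 5% level and any multiplicity rule may stand in a statistical analysis plan not shown here.

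Finally, it would be too strong to say that MACE cannot inform. The composite includes repeated hospitalization, its rate is unknown, and an interval estimate is useful even when power is low.

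These points narrow the claim but do not remove it. Which outcome decides the trial's question is a protocol choice. A later analysis plan details the analysis of a primary outcome but is not normally where that outcome is first chosen.

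**Conclusion.** The concern holds in this limited form: no primary outcome, no adopted definition of remodeling, and no between-dose contrast. The dose conclusion is therefore open to selection after the fact. Under unadjusted two-sided 5% tests, the chance of at least one false dose difference is well above 5% throughout. It is about 9–10% for two outcomes at correlations up to 0.5, about 25–51% for the aim's own family of roughly 14 measures, and 33–75% for all of about 27. The last two ranges run from correlation 0.7 down to 0. The significance level, the correlations, the equal allocation and the MACE rates are all assumptions. At an assumed 20% rate, MACE could reliably show only very large dose differences. The plan should be changed, and the change is cheap.

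**What to change.** Before the first 6-month echo, amend sections 2 and 5 as follows.

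- Name one primary outcome, with its definition, time point and contrast. One option is the 10 mg versus 25 mg difference at 6 months in a single continuous LV measure, tested once at two-sided 5%. Biplane Simpson EF is already listed; end-systolic volume could be taken from the same tracings.
- State how patients who die or have no 6-month echo enter that analysis. Without this rule the primary outcome is undefined for them, and the 0.40 SD figure is slightly optimistic.
- Make MACE the key secondary outcome, reported as a risk difference with 95% CI.
- Label all other echo parameters exploratory, with no significance claim.
- Write the between-dose contrast into section 5 beside the existing day-one versus 6-month comparison.

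The cost is protocol wording and one decision on missing echoes; no new imaging is needed. There are two downsides. Isolated significant results on other parameters can no longer be presented as the trial's conclusion. The primary outcome would also be an imaging measure rather than a clinical event, a judgement that the investigators should make openly.

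### Does counting new-onset heart failure in MACE fail because heart-failure status at entry is not a named baseline item and the event window cites two starting events?

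*Protocol*

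**What the plan says.** The aim (section 2) is to compare two empagliflozin doses for MACE and LV remodeling in "diabetic patients with Anterior STEMI with reduced LVEF who underwent PPCI". The passages that bear on this point are:

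- **Endpoint (section 4, G).** MACE is a "composite point of death, repeated hospitalization, re-infarction and new onset heart failure", "observed for six months post catheterization and initiation of SGLTi". No criteria are given for any component.
- **Follow-up (section 4, H).** Here "patients will be followed up for 6 months regarding symptoms and MACE", and all echocardiographic parameters are repeated at the end.
- **Exclusions (section 3).** The nearest ones are valvular disease and "Patients with LV myopathies of non-ischemic origin". Earlier ischemic heart failure is not excluded.
- **Baseline data (section 4, A and B).** The history covers "past history with special comment on diabetes and other comorbidities e.g hypertension, CKD and dyslipidemia", together with present illness and drug history. The examination covers vital signs and heart and chest auscultation.
- **Heart-failure wording (section 4, D).** "Heart failure with reduced ejection fraction (HFrEF) was defined as EF less than 40" per cent, with a guideline citation.
- **Background.** The outcome trial cited there is said to have been driven by "a reduction in cardiovascular deaths and hospitalization for heart failure".

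**The concern.** A component that counts only first occurrences needs a record of who already had the condition. These patients are selected for reduced LVEF after an anterior infarction, so heart failure at entry is a realistic possibility, and heart failure is not among the named comorbidities. An SAP can settle event wording later, but it cannot restore day-one information that was never collected. The background also gives heart-failure hospitalization as a main reason for using this drug class, so the component matters.

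Three further points add to the worry:

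- The only numerical heart-failure definition in the protocol is EF below 40%. If it governed MACE and if reduced LVEF at entry meant the same cut-off, no patient could have a new onset.
- The window names two starting events and gives no interval between them.
- Repeated hospitalization could mean one readmission or at least two, and planned admissions are not addressed.

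At stake would be a component scored differently from patient to patient, with no means of repair at analysis.

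**Working it through.** The protocol gives no event rate, effect size or power, so there is no figure of its own to reproduce. The check is mainly a comparison of passages. The arithmetic below is illustrative and rests on assumed inputs.

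**1. Is status at entry likely to be captured?** The comorbidity list is introduced as examples, so prior heart failure belongs under it without any stretch. Present illness and drug history bear on both prior and current heart failure, and auscultation bears on signs at the index admission. The same history and examination are taken whatever the dose. EF is not the only relevant measure taken at both times: item H repeats every echocardiographic parameter, which includes E/E' and global longitudinal strain. These do not settle clinical status alone, but baseline cardiac function is well documented.

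**2. Does the EF definition defeat the component?** Only if it is applied to MACE, and no passage applies it. It stands among cited background remarks in the echocardiography section. Item H follows patients for symptoms, which points to a clinical reading, under which a new onset can occur.

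**3. How many patients could be affected?** Let p be the assumed share entering with heart failure. The number at risk of a first onset is 200 × (1 − p):

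- p = 10%: 200 × 0.90 = 180 at risk, 20 not
- p = 25%: 200 × 0.75 = 150 at risk, 50 not
- p = 50%: 200 × 0.50 = 100 at risk, 100 not

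If the groups were 100 each and formed at random (neither is stated), the difference in such patients between groups has SD = √(2 × 100 × p × (1 − p)):

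- p = 10%: √18 = 4.24; × 1.96 = 8.3 patients
- p = 25%: √37.5 = 6.12; × 1.96 = 12.0 patients
- p = 50%: √50 = 7.07; × 1.96 = 13.9 patients

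This is ordinary chance imbalance. It arises whether or not status is written down, so it does not measure the cost of the omission.

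**4. What happens to the composite?** Assume the other components occur in 15% v 10%, and new heart failure in 18% v 9% of those at risk, independently. The composite is 1 − (1 − other) × (1 − HF × (1 − p)):

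- p = 0: 1 − 0.85 × 0.82 = 30.3% v 1 − 0.90 × 0.91 = 18.1%
- p = 25%: 26.5% v 16.1%
- p = 50%: 22.7% v 14.1%

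Power at 100 per group, two-sided 0.05, falls from 52% to 44% and 35%. The fall comes from enrolling patients who cannot have a first onset. Recording their status would not reverse it.

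**5. Does another component cover the gap?** Repeated hospitalization is itself part of MACE. If it is read as one or more readmissions, a readmission for pre-existing heart failure already counts. Status at entry then decides the composite only for heart failure without readmission, including onset during the index stay. Under the reading of at least two admissions, the cover is weaker.

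**6. How much does the start of the window matter?** Taking six months as 182 days, an assumed gap between catheterization and first dose of 0, 1, 3, 7 or 14 days shifts the start by 0%, 0.5%, 1.6%, 3.8% or 7.7% of the window (for example 7/182 = 3.8%). These are shares of time, not of events. If the first dose is given on the day of catheterization, the question disappears.

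**The case for a change.** The strongest case for a change is that the protocol itself sets both the endpoint and the baseline list, and that the two do not visibly match. Data never required cannot be recovered, whereas two or three fields on the day-one form cost almost nothing. Optional recording may also vary between assessors, and an event that is new by definition deserves a fixed reference.

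The textual observation stands: prior ischemic heart failure may enter, and heart failure is not named at baseline. The point about variation between assessors also has some force.

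The step from *not named* to *not collected* does not stand. The list is open, the required history and examination cover the ground, and the case report form is not shown and cannot be judged incomplete. The EF argument depends on a link the text never makes. The window wording puts both events before the start of counting, and no passage implies a gap. The meaning of repeated hospitalization, the start date and the event criteria are details commonly fixed in an SAP, which may exist but was not available here. Scoring heart failure clinically, or separating onset from worsening, would be a preference about the endpoint and would correct no error.

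**Conclusion.** No change to the plan follows. This is a gap that investigators and analysts would fill sensibly: ask about prior heart failure under comorbidities, note symptoms and signs at the index admission, and open the event window once both catheterization and first dose have occurred. No stated rule or figure in the protocol is shown to give a wrong result.

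The size of any effect on the dose comparison cannot be derived from the document. The 20, 50 or 100 patients not at risk rest on assumed shares of 10%, 25% and 50%. The chance imbalance of about 8, 12 or 14 patients also assumes equal, randomly formed groups. Neither quantity depends on whether the baseline item is named.

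The conclusion assumes that the required history and examination are done and written down, and that MACE heart failure is judged clinically, as follow-up for symptoms suggests. Naming heart-failure status explicitly on the day-one form would be a useful minor clarification, so that both dose groups are judged alike, but the plan works without it.

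### Does a 6-month study period, with the final echo at its end, give patients unequal follow-up?

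*Protocol*

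**What the plan says.** The relevant statements are spread over four sections of the protocol.

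- **Section 2 (Aim/Objectives):** the two doses are compared "regarding MACE and LV remodeling for 6 months duration".
- **Section 3 (Methodology):** the duration entry reads "Study Period: 6 months". The sample is 200 patients in two groups, described as "Patients diagnosed with anterior STEMI in the ER fulfilling the inclusion criteria". No accrual period is given.
- **Section 4, item G (MACE):** the composite "will be observed for six months post catheterization and initiation of SGLTi".
- **Section 4, item H (Follow up):** "patients will be followed up for 6 months regarding symptoms and MACE". The next sentence reads "All echocardiographic study parameters will be repeated at the end of the study period".
- **Section 5 (Statistical Analysis):** the data will be analyzed to "compare results in different time (day one then 6 months later".

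**The concern.** The duration entry in Section 3 stands beside study type, setting and sample size, where a trial's overall calendar length is usually given. Read that way, it conflicts with Section 4 item H. Patients with an acute infarction enter as they present, and 6 months of follow-up each fits inside a 6-month study only if all 200 enter on one day. The final echo is tied to the end of that period, so a patient enrolled at month 4 would be imaged at 2 months.

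This would matter because remodeling depends on time since infarction. The remodeling cut-off quoted in Section 4 item D is itself tied to imaging at a stated interval after the infarct. Echoes taken at mixed intervals would not give the comparison that Section 5 describes. If MACE observation also stopped at a common date, events would be under-counted. Crude proportions would also be distorted if one dose group were enrolled before the other.

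A second worry is that item G names two starting events, catheterization and drug initiation, with no stated interval between them. Because inclusion requires patients to be receiving the drug, time before the first dose might be protected from events.

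**Working it through.** The protocol gives no follow-up figure to reproduce beyond the 6 months itself. The check is to work out what each reading implies and then see which one the text supports.

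**Inputs from the protocol:** 200 patients; study period 6 months; follow-up 6 months per patient; MACE window 6 months; analysis at day one and 6 months later. **Assumptions, not in the protocol:** uniform accrual over *a* months and, for the event figures, a constant hazard and a chosen 6-month risk.

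**Reading 1: a 6-month calendar study with one closing date.** Follow-up runs from 6 − *a* to 6 months, with mean 6 − *a*/2. Patient-time is 200 × (6 − *a*/2). Giving everyone a full 6 months would need 6 + *a* calendar months.

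| Accrual *a* (months) | Shortest follow-up | Mean follow-up | Patient-months | Share of 1200 | Calendar months needed |
|---|---|---|---|---|---|
| 1 | 5 | 5.5 | 1100 | 92% | 7 |
| 3 | 3 | 4.5 | 900 | 75% | 9 |
| 6 | 0 | 3.0 | 600 | 50% | 12 |

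For MACE at *a* = 6, let *R* be the true 6-month risk and *h* = −ln(1 − *R*)/6. The average observed risk is 1 − (1 − e^(−6h))/(6h) = 1 − *R*/(−ln(1 − *R*)).

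- *R* = 0.20: 1 − 0.20/0.2231 = 0.104.
- *R* = 0.30: 1 − 0.30/0.3567 = 0.159.

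If one group filled in months 0–3 and the other in months 3–6, mean follow-up would be 4.5 and 1.5 months.

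**Reading 2: six months for each patient.** Follow-up is 6 months for all, 200 × 6 = 1200 patient-months before deaths and losses. There is no variation by design, whatever *a* is.

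**Which reading the text supports**

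1. Item G counts MACE from the patient's own procedure and drug start. A common closing date cannot be reconciled with that.
2. Item H gives patients, not the study, 6 months of follow-up. The echo sentence comes directly after it, so the end of the period most naturally means the end of those 6 months.
3. Section 5 fixes the comparison at day one and 6 months later, which is a per-patient interval.
4. The aim gives 6 months as the duration over which both MACE and remodeling are compared.
5. Section 4 item C schedules an ECG for all patients at the start of the study. For patients who have not yet had their infarct on the opening date, that can only mean each patient's own start.

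Only the duration entry in Section 3 suggests a calendar period, and it too can be read as time on study.

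**The two MACE origins.** If the first dose comes *g* days after catheterization, the window runs either from day 0 to month 6 or from day *g* to month 6 plus *g* days. Its length is 6 months in both cases. Both groups receive the drug, so any requirement to reach the first dose applies to both. The protocol states no gap and gives no reason for it to differ by dose.

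**The case for a change.** The strongest case for acting is that visit timing, study duration and day 0 belong in a protocol, and that the literal wording allows a harmful reading. If the Section 3 entry is a calendar period, the follow-up in item H cannot be delivered. If it is a per-patient period, accrual is stated nowhere and the echo is tied to an awkward phrase. A correction would need only wording, with no extra patients or visits. Because no allocation method is described, filling the groups in sequence is not excluded. In that case a true 20% risk in both groups would appear as about 15.4% and 5.4% under a common closing date.

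Part of this stands. A 6-month calendar study cannot hold staggered entry plus 6 months of follow-up each, and the accrual period is indeed absent.

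The consequences do not stand. The phrase about the end of the study period governs only the repeat echo. To obtain 10.4% for 20%, or 15.9% for 30%, one must let a one-line duration entry override the explicit MACE window in item G and the follow-up statement in item H. One must also assume accrual spread over the full 6 months. The sequential-fill figures further require an enrolment order that the protocol does not state: calling one group the first is a label. How patients are allocated is a separate question and cannot be used to enlarge this one. The protected-time argument is also overstated. Receiving the drug requires survival to the first dose, but it does not rule out an earlier re-infarction or new heart failure, and a difference between doses is speculation.

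**Conclusion.** The concern does not hold as a defect that calls for a change. The wording of the study period and of day 0 is loose, but the aim, the MACE definition, the follow-up paragraph and the statistical section all give each patient a fixed 6 months. On that reading follow-up is equal, and the final echo falls at the time the analysis needs. The shortfalls in the calendar reading (mean follow-up of 5.5 to 3.0 months for accrual over 1 to 6 months) describe a plan the protocol does not set out. The MACE figures rest further on assumed risks and on a stopping rule that contradicts item G.

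The two MACE origins leave the window's length unchanged. Their effect is limited to a shift equal to the gap between procedure and first dose, which the protocol does not give. The unstated accrual period affects how long the centre must run the study, not what is measured on any patient. This is a gap that investigators and analysts would fill sensibly from the protocol's own statements, and spelling it out would alter no result.

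The conclusion assumes that sites apply the 6 months to each patient, as sections 4 and 5 indicate.
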